Steering Committee	
Academic Centre for General Practice, KU Leuven [name] [name], [name] [name] [name] [name] Belgium
 
Department of Family Medicine and Primary Health Care, Ghent University [name] [name] [name] [name]
 
Department of General Practice, U Antwerp [name], [name]

[name]
[name]
[name]

Vakgroep Huisartsgeneeskunde, VUB
[name] [name]
[name]
[name]

UR Soins primaires et Santé, Liège Université
[name] [name], [name]
[name]
[name]

Département de Médecine générale, ULB
[name]. [name], [name]
[name]
[name]
[name]

KCE, Federaal kenniscentrum voor de gezondheidszorg
[name] or representative
[name]
[name]

Clinical Trial Unit (CTC), UZ Leuven
UZ Leuven
[name]
[name]

Leuven Biostatistics and Statistical Bioinformatics Centre, KU Leuven
[name]
[name]
[name]

Algemeen Medisch Labo (AML)
[name]
[contact]
[name]
[name]

Clinical Pharmacology – Department of Pharmacology, UGent
[name] [name]
[contact]
[name]
[name]

Trefpunt Zelfhulp
[contact]

	
[name] [name]
 
Patient involvement [name] and [name]

--	---

TRIAL SUMMARY

Trial Title	The effectiveness of a blended care program for the discontinuation of benzodiazepines use for sleeping problems in primary care: a clustered randomized trial.	
Short Title	Blended care for the discontinuation of benzodiazepine use: Big Bird trial	
Trial Design	Cluster randomized controlled trial	
Trial Participants	Primary care patients aged 18 and older receiving prescriptions for (z-) benzodiazepines ((z-)BZD) for daily use in the last 6 months for a primary indication of sleeping problems.	
Planned Sample Size	120 general practitioners randomised, each recruiting 10 patients, totalling 1200 patients	
Treatment duration	1-6 months	
Follow up duration	12 months	
Planned Trial Period	42 months	
	Objectives	Endpoints

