4 TRIAL DESIGN

This study is a pragmatic cluster randomised controlled superiority trial:

multi-centre: 6 academic centres of general practice will be involved in the recruitment of 120 GPs primary care practices

pragmatic: criteria excluding patients from participation will be limited as well as procedures that do not reflect care as usual

cluster: randomisation occurs at the level of the primary care practice while patients are the unit of analysis

randomised: block randomization per academic centre will be performed to assign primary care practices to either the intervention or the control arm

controlled: the intervention will be compared with usual care

superiority: the trial is designed to show that the intervention is superior to usual care

The rationale for choosing a cluster design is to prevent contamination across the intervention and control arm. The cluster and unit of randomization is the primary care practice. There will be 2 arms – the blended care arm and the usual care arm- in 50:50 ratio.

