7 TRIAL PROCEDURES

7.1 Recruitment

For the recruitment of GPs, each academic centre will regionally organise training and education sessions on the management of withdrawal of (z-)BZDs and invite GPs to attend one of these. These two-hour sessions aim to refresh and train GPs' knowledge and skills on (z-)BZD discontinuation rather than to teach new information and skills.

Specifically, the training sessions will consist of an existing educational package on benzodiazepine withdrawal that was developed by the Project Group Benzodiazepines and commissioned and financed by the Federal Public Service Health. These trainings available in French and Dutch are typically delivered by a trained GP and psychologist.

The content of these sessions cover non-pharmacological minimal interventions and extended interventions and pharmacological approaches for (z-)BZD tapering and withdrawal and are based on the contents of

- “Anxiety, stress and sleeping problems. A toolbook for general practitioners” which was developed in 2005 by order of the Belgian Government as part of the fourth national campaign for a responsible use of (z-)BZD.
- The online guideline “Sleeping pill and sedatives. How to assist your patients in their search for other solutions” which was developed as part of the latest (2018) national campaign for a responsible use of (z-)BZD. Both toolboxes are available in French, Dutch.

At the end of the sessions attending GPs will be invited to participate in the study.

7.1.1 *Patient identification*

The participating GPs will be asked to recruit consecutively 10 patients consulting for benzodiazepine prescription renewal, during a period of maximum 6 weeks. This is feasible since assuming that 10% of the population takes (z-)BZDs on a regular basis –a conservative estimate- and assuming prescriptions are provided on a bi-monthly basis, full time working GPs see monthly between 50 and 150 patients for (z-)BZD prescription renewals (depending on the patient load varying between 1000 and 3000).

During this period of 6 weeks, the GP will keep a list of the number of eligible patients consulting for a BZD prescription renewal and will tally whether they were invited to participate in the study or not. In the latter case the GP will be asked to give the reason why he/she did not do so. Also when a patient declines participation in the study, the GP will ask for and record the reason of refusal.

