7.3 The randomisation scheme

In order to avoid contamination between GPs working in the same practice randomization will happen at the level of general practice.

General practices will be randomized in one of the 2 study arms in a 1:1 ratio using a block randomization system stratified per language in order to guarantee that allocation to either usual care or blended care for the discontinuation of (z-)BZD is balanced between communities.

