10 STATISTICS AND DATA ANALYSIS

10.1 Sample size calculation

The primary research question driving the sample size calculation is whether chronic benzodiazepine users who receive the blended learning intervention are more likely to discontinue (z-)BZD use at 12 months follow-up compared to chronic benzodiazepine users who receive usual care.

The rate of discontinuation by usual care is expected, based on a literature review of RCTs to achieve a rate ranging between 10 and 17%. (Mugunthan K, McGuire T and Glasziou P. Minimal interventions to decrease long-term use of benzodiazepines in primary care: a systematic review and meta-analysis. Br J Gen Pract 2011; 61 (590): e573-e578.)

The study will be powered to detect a statistically significant difference in (z-)BZD discontinuation at 12 months between intervention and control group of 10%, assuming a rate of discontinuation of 15% in the control group

Based on an alpha of 0.05 and 80% power and assuming 10% patients lost to follow-up (In the study by Vicens et al the drop-out rate after 12 months was 7%) an individually randomized study would require a total sample size of 594 participants (297 in each group).

To account for clustering effects from randomized GPs with an intracluster correlation coefficient (ICC) set at 0.11 based on a study by Vicens et al. (C. Vicens, F. Bejarano, E. Sempere, et al. Comparative efficacy of two interventions to discontinue long-term (z-)BZD use: cluster randomized controlled trial in primary care. The British Journal of Psychiatry (2014) 204, 471–479.) and a cluster size of 10 patients, the number of patients required was multiplied by 1.99 corresponding to the cluster design effect ($DE=1+ICC(\text{size of the cluster}-1)$). Thus, the final sample will consist of 1182 patients. Because each general practitioner has to recruit 10 patients, 119 general practitioners are needed.

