10.2 Planned recruitment rate

The centres for general practice of KU Leuven, U Ghent, U Antwerp, ULB, VUB and U Liège will each recruit 20 GPs for participation in the trial within a period of 6 months. In case one of the academic centres for general practice fails to reach this goal another centre will be requested to recruit more general practices.

After 3 months, all GPs will have enrolled 10 patients. Taking the high prevalence of BZD use into account there will not be any difficulty in finding enough eligible patients in GP practices included in the study (see 7.1.1 Patient identification).

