10.3.2 Primary outcome analysis

The primary endpoint will be analyzed according to the intent-to-treat (ITT) approach.

Logistic regression will be used for data analysis with negative benzodiazepine urine test assessed 12 months after initiation of the intervention as a binary outcome and intervention group as a factor. A random effect will be modelled to deal with clustering by general practitioner. The group effect will be reported as an odds ratio with 95% confidence interval.

Subgroup analysis will be performed in order to investigate how the primary outcome behaves in function of:

- age categories
- gender
- (z)BZD dose at baseline in DDD
- Sleep quality at baseline
- Benzodiazepine dependency score
- For the intervention group only: use of e-tool

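### Practices are randomised, but the outcome models and the design effect stop at the GP, so the primary confidence interval is too narrow wherever a practice enters several GPs with positively correlated patients

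*Combined protocol and SAP*

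**What the plan says.** - **Randomised unit.** Section 4: "The cluster and unit of randomization is the primary care practice". Section 7.3 gives the reason: "In order to avoid contamination between GPs working in the same practice randomization will happen at the level of general practice". Section 7.7 allocates the practice once its GP or GPs have enrolled the tenth patient, so practices with several participating GPs are foreseen.
- **Primary model.** Section 10.3.2: "A random effect will be modelled to deal with clustering by general practitioner". No practice term is mentioned.
- **Secondary models.** Section 10.3.3 analyses the 6-month urine test in the same way. The longitudinal models have random intercepts for patient and GP only.
- **Sample size.** Section 10.1 builds its design effect on GPs: "To account for clustering effects from randomized GPs with an intracluster correlation coefficient (ICC) set at 0.11". It concludes: "Because each general practitioner has to recruit 10 patients, 119 general practitioners are needed".
- **Patients per unit.** The trial summary has "120 general practitioners randomised, each recruiting 10 patients, totalling 1200 patients". Section 7.1.1 has "The participating GPs will be asked to recruit consecutively 10 patients consulting for benzodiazepine prescription renewal", and section 10.2 has "After 3 months, all GPs will have enrolled 10 patients". Section 7.3.1, by contrast, waits for 10 patients in the general practice before allocating it, and section 7.7 appears to read the same way. Section 7.3.1 also counts its blocks in GPs although practices are allocated.

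**The concern.** All GPs of a practice receive the same arm. A model with a GP intercept and no practice intercept treats two colleagues as if they had been allocated independently. If their patients resemble each other more than patients of different practices do, that shared variation goes straight into the treatment contrast, and the model does not count it. The standard error of the primary odds ratio is then too small, its 95% interval too narrow, and the false-positive rate above 5%. This is the anti-conservative direction in a superiority trial.

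The sample size has a related problem. If each GP recruits 10 patients, a practice with two GPs is a randomised cluster of 20, and a design effect computed for clusters of 10 is too small whenever the between-GP correlation is positive.

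**Working it through.** **Inputs from section 10.1:** 15% v 25% discontinuation, alpha 0.05, power 80%, 10% loss, ICC 0.11, cluster size 10.

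**The plan's own figures reproduce.** The two-sided two-proportion formula with continuity correction gives 270 per arm. Then 270 × 1.10 = 297 per arm, or 594 in total. The design effect is 1 + 0.11 × 9 = 1.99, and 594 × 1.99 = 1182. Finally 1182 / 10 = 118.2, so 119 GPs.

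**Assumptions not in the plan:** the number k of GPs per practice, and the correlation r between patients of different GPs in one practice. The within-GP ICC stays at 0.11, and r is taken as 0.02, 0.055 and 0.11.

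**Formulas.** With m patients per GP:

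- the GP-only model assumes DE_GP = 1 + (m − 1) × 0.11;
- the true factor is DE = DE_GP + (k − 1) × m × r;
- the actual two-sided error is P(|Z| > 1.96 / √(DE / DE_GP)).

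Where only a share f of GPs sits in two-GP practices, the average is DE = 1.99 + f × 10 × r.

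| Scenario | Assumed DE | True DE (r = 0.02 / 0.055 / 0.11) | Actual error |
|---|---|---|---|
| (a) All practices with 2 GPs, 10 patients per GP | 1.99 | 2.19 / 2.54 / 3.09 | 6.2% / 8.3% / 11.6% |
| (b) Half the GPs in 2-GP practices, 10 per GP | 1.99 | 2.09 / 2.265 / 2.54 | 5.6% / 6.6% / 8.3% |
| (c) 10 per practice, shared by 2 GPs | 1.44 | 1.54 / 1.715 / 1.99 | 5.8% / 7.3% / 9.5% |
| A quarter of the GPs in 2-GP practices, 10 per GP | 1.99 | 2.04 / 2.13 / 2.265 | 5.3% / 5.8% / 6.6% |
| A tenth of the GPs in 2-GP practices, 10 per GP | 1.99 | 2.01 / 2.045 / 2.10 | 5.1% / 5.3% / 5.6% |
| One GP per practice, or r = 0 | – | equal to assumed | 5.0% |

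Worked example, (a) with r = 0.055: DE = 1.99 + 10 × 0.055 = 2.54; 2.54 / 1.99 = 1.28; 1.96 / √1.28 = 1.73; two-sided tail 8.3%.

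**Simulation of the planned model.** This was a random-intercept logistic model with a Wald test, a null rate of 15%, 1,200 patients and 4,000 runs per scenario (Monte Carlo error about 0.4 points). In (a) the GP-only model rejected 5.8% at r = 0, then 6.4% at 0.02, 8.9% at 0.05 and 11.6% at 0.11. In (b) it rejected 6.9% at 0.05 and 8.9% at 0.11; in (c), 7.6% and 9.0%. With a practice intercept instead, the rate stayed between 4.8% and 6.3% in all eight scenarios. A separate simulation of cluster-level t-tests (20,000 trials per scenario, two or three GPs per practice, r from 0.02 to 0.08) gave 6.2% to 11.1% when GPs were the unit and 4.7% to 5.1% when practices were.

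**Power of a valid practice-level analysis, if the 10 patients are per GP.** Effective n per arm = 1182 × 0.9 / DE / 2.

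| DE | Where it arises | Effective n per arm | Power, with continuity correction | Power, without |
|---|---|---|---|---|
| 1.99 | as planned | 267 | 79.6% | 82.6% |
| 2.19 | (a), r = 0.02 | 243 | 75.4% | 78.9% |
| 2.265 | (b), r = 0.055 | 235 | 73.8% | 77.5% |
| 2.54 | (a), r = 0.055; (b), r = 0.11 | 209 | 68.4% | 72.7% |
| 3.09 | (a), r = 0.11 | 172 | 59.0% | 64.1% |

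If instead the 10 are per practice and about 119 practices enrol, the practice-level DE is at most 1 + 9 × 0.11 = 1.99. The power then holds, but the error rates in (c) remain.

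**The case against.** The strongest reply is that the plan uses GP and practice interchangeably. The trial summary and section 10.1 speak of GPs being randomised, section 7.3.1 counts blocks in GPs, and section 10.2 has centres recruit GPs but make up a shortfall with general practices. If the GP in sections 10.3.2 and 10.3.3 means the allocated unit, the model is at the right level and only the wording is at fault. That reading is possible. But section 7.3 explicitly distinguishes GPs from the practice they share, and nothing defines one as the other or limits a practice to one GP.

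A second point is that the upper figures come from heavy assumptions: every GP in a two-GP practice, and a between-GP correlation as large as the within-GP one. This is fair. At a tenth to a quarter of GPs in such practices the error is only 5.1% to 6.6%. The simulation also cannot separate r = 0.02 from r = 0, since 6.4% against a baseline of 5.8% is within noise. The excess may be small.

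Third, a nested GP term may be poorly estimable if most practices enter one GP, and in the longitudinal models it adds a level. This also stands. The practice intercept carries the correction, and the GP term can be dropped if it cannot be estimated.

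**Conclusion.** The concern holds in its conditional form. The cluster term sits below the randomised unit, and the plan does not rule out the situation in which that matters. The interval is too narrow whenever some practices enter several GPs and their patients are positively correlated, whether the 10 patients are per GP or per practice. The size cannot be fixed from the plan. Over the assumed range the actual error runs from barely above 5% to 11.6%, with no excess if every practice enters one GP or the between-GP correlation is zero. The power loss applies only if the 10 patients are per GP: from 80% down to between 75% and 59% with two GPs in every practice, using the plan's continuity correction. The contradiction over 10 patients per GP or per practice needs resolving in any case. Because this concerns the primary confidence interval, and choosing the cluster level after seeing the data would be post hoc, it should be settled before analysis.

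**What to change.** - **Sections 10.3.2 and 10.3.3:** specify a random intercept for the general practice, with GP nested within practice where a practice has more than one GP. State in advance that the GP term is dropped if it is not estimable.
- **Section 10.1:** reconcile with the trial summary and sections 7.1.1, 7.3.1, 7.7 and 10.2 whether 10 patients is per GP or per practice. Compute the design effect at practice level from the expected number of patients per practice, and restate the power.
- **Section 7.3.1:** state the block sizes in practices.
- If the GP is meant as shorthand for the practice, or each practice enters exactly one GP, say so explicitly.

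The cost is wording plus a practice identifier already known at randomisation. No cap on GPs or patients per practice and no extra enrolment is proposed. The confidence interval may be slightly wider, and if the 10 patients are per GP the stated power will look less favourable.

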10.3.3 Secondary outcome analysis

The proportion of subjects with a negative benzodiazepine urine test assessed 6 months after initiation of the intervention will be analyzed in the same way as the primary endpoint.

All other secondary endpoints are binary variables, measured longitudinally. Analysis will be performed using multilevel logistic regression analysis, including random intercepts for patient and for general practitioner. A random slope for time will be modelled if beneficial for model fit. The fixed effects model will include intervention group, time and the group by time interaction. In case of a significant group by time interaction, the group effect will be reported separately for each time point. In case of a non-significant group by time interaction, a group main effect will be reported. The group effects will be presented as odds ratios with 95% confidence intervals.

The EQ-5D-3L data will be summarized based on the principles of a Pareto improvement in Welfare Economics - the Pareto Classification of Health Change (PCHC) (Devlin 2010). According to this principle an EQ-5D-3L health state is deemed to be 'better' than another if it is better on at least one dimension, and is no worse in any other dimension. And an EQ-5D-3L health state is deemed to be 'worse' than another if it is worse in at least one dimension, and is no better in any other dimension. Using that principle to compare a patient's EQ-5D-3L health states between any 2 time periods, there are only 4 possibilities:

- Their health state is better
- Their health state is worse
- Their health state is exactly the same
- The changes in health are 'mixed': better on one dimension, but worse on another.

The EQ-5D-3L scores will be analyzed as (1) better versus other, and (2) worse versus other.

No correction for multiplicity is planned for the secondary analyses, as the study is not powered for these analyses, and hence, its results will be considered as hypothesis generating.

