Primary	To compare the long-term effect of a blended care approach (interactive learning e-tool and face-to-face contacts with general practitioner) versus usual care on the discontinuation of (z-)BZD	Proportion of patients that discontinued (z-)BZD use at 12 months assessed by toxicological screening
Secondary	To compare the short-term effect of a blended care approach (interactive learning e-tool and face-to-face contacts with GP) versus usual care on the discontinuation of (z-)BZD	Proportion of patients that discontinued (z-)BZD use at 6 months assessed by toxicological screening
	To compare the effect of a blended care approach (interactive learning e-tool and face-to-face contacts with GP) versus usual care on the quality of life	EQ5D-3L assessed at week 6, 12, 26 and 52

	To compare the effect of a blended care approach (interactive learning e-tool and face-to-face contacts with GP) versus usual care on self-reported discontinuation of (z-)BZD use	Proportion of patients with self-reported discontinuation of (z-)BZD use assessed at week 6, 12, 26 and 52
	To compare the effect of a blended care approach (interactive learning e-tool and face-to-face contacts with GP) versus usual care on the number of defined daily doses (DDD) of benzodiazepines prescribed	The number of DDD of (z-)BZD prescribed in the preceding interval assessed at week 6,12,26 and 52

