3.1.4 Prescriptions for benzodiazepines

The fourth secondary objective is to compare the effect of blended care combining an interactive educational e-tool with face-to-face clinical consultations versus usual care on the number of DDD of (z-)BZD prescribed at 6, 12, 26 and 52 weeks from baseline in a population of adult primary care patients chronically using benzodiazepines for a primary indication of sleeping disorders.

Null hypothesis: blended care is not superior to usual care in terms the number of DDD of benzodiazepines prescribed at 6, 12, 26 and 52 weeks from baseline.

Alternative hypothesis: blended care will decrease the number of DDD of (z-)BZD prescribed at 6, 12, 26 and 52 weeks from baseline compared to usual care.

PICOT

Population: Patients receiving prescriptions for (z-)BZD on a daily basis in the last 6 months for a primary indication of sleeping problems aged 18 and older.

Intervention Blended care combining an interactive educational e-tool with face-to-face clinical consultations with the GP.

Comparator Care as usual for chronic (z-)BZD use left at the discretion of the GP. This may include a minimal intervention (discontinuation letter or discontinuation advice) or a more extended intervention, in combination with (z-)BZD tapering.

Outcome The number of DDD of (z-)BZD prescribed.

Time The outcome will be assessed 6, 12, 26 and 52 weeks after initiation of the intervention.

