3.5 Secondary endpoints

- The proportion of subjects with a negative benzodiazepine urine test assessed 6 months after initiation of the intervention.
- The proportion with a better score in quality of life from baseline to 6, 12, 26 and 52 weeks.

- The proportion of subjects that self-report to have ceased benzodiazepine use at 6, 12, 26 and 52 weeks.
- The number of DDD of benzodiazepines prescribed at 6, 12, 26 and 52 weeks from baseline.

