10.3 Statistical analysis plan

10.3.1 Summary of baseline data and flow of patients

Presentation of baseline characteristics of the study population and comparability of the 2 arms will be based on the following variables:

- Age (mean and standard deviation or median and 25-75 percentiles)
- Gender (percentage)
- Relevant co-morbidities (percentage)
- Benzodiazepine dependence score (means and standard deviation or median and 25-75 percentiles)
- Daily dose of (z)BZD in DDD (means and standard deviation or median and 25-75 percentiles)
- Sleep quality
- Audit-C score

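### Section 10.3.3 treats every remaining secondary endpoint as binary, but the number of DDD prescribed is a quantity with no cut-point, so the assigned logistic model cannot test objective 3.1.4 as worded

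*Combined protocol and SAP*

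**What the plan says.** Section 3.5 lists four secondary endpoints. Section 10.3.3 analyses the first, the 6-month urine test, like the primary endpoint. For the rest it says "All other secondary endpoints are binary variables, measured longitudinally". It prescribes multilevel logistic regression with random intercepts for patient and general practitioner, fixed effects for group, time and their interaction, and a random slope for time if that improves fit. It then adds "The group effects will be presented as odds ratios with 95% confidence intervals".

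The three endpoints covered by that sentence are defined as follows:

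- Self-report, section 3.5: "The proportion of subjects that self-report to have ceased benzodiazepine use at 6, 12, 26 and 52 weeks".
- Quality of life: section 3.5 gives the proportion with a better score, and section 10.3.3 gives the coding: "The EQ-5D-3L scores will be analyzed as (1) better versus other, and (2) worse versus other".
- Prescriptions, section 3.5: "The number of DDD of benzodiazepines prescribed at 6, 12, 26 and 52 weeks from baseline". The trial summary words it as "The number of DDD of (z-)BZD prescribed in the preceding interval assessed at week 6,12,26 and 52". The alternative hypothesis in 3.1.4 is that "blended care will decrease the number of DDD of (z-)BZD prescribed at 6, 12, 26 and 52 weeks from baseline compared to usual care".

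**The concern.** A logistic model needs a yes/no outcome. The DDD endpoint is an amount, and its hypothesis concerns a fall in that amount. Without a threshold the model cannot be fitted. With a threshold chosen later, it would compare the proportion of patients beyond that threshold, which is a different question from the one in 3.1.4.

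What is at stake is pre-specification of one secondary objective. The random effects, the interaction rule and, in the trial summary, the prescribing window are already written. The outcome distribution or cut-point, and with it the effect measure, is not. As the plan stands, the analyst would have to choose these after the data are in.

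**Working it through.** The plan states no figure for this endpoint. Its one calculated figure, the sample size in section 10.1, concerns the primary endpoint and has no bearing here. The check is therefore mainly a comparison of sections.

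**1. Which endpoints does the sentence cover?** Section 3.5 lists 4 secondary endpoints. Removing the 6-month urine test leaves 4 − 1 = 3.

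| Endpoint | As defined | Rule making it binary | Suits logistic regression? |
|---|---|---|---|
| Self-reported cessation | Proportion who stopped (3.5) | Not needed | Yes |
| EQ-5D-3L | Proportion with a better score (3.5) | Better versus other; worse versus other (10.3.3) | Yes |
| DDD prescribed | Number (trial summary, 3.1.4, 3.5) | None | No |

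Two of the three are binary and one is not.

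**2. Is DDD made binary anywhere?** No section gives a cut-point, a responder definition or an alternative model. Section 10.3.1 summarises baseline daily dose in DDD by mean and standard deviation, or by median and quartiles. That is a related variable, not the endpoint itself, but it shows DDD being handled as a quantity.

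**3. Could zero versus any prescribing be the implied split?** The plan does not say so, and it would not match 3.1.4. Section 8.1 describes a typical taper of 10–20% of daily dose every 2–4 weeks. Taking the fastest end purely as an illustration, about three steps of 20% fit into the first 6 weeks:

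- each step a share of the starting dose: 3 × 20% = 60% reduction;
- each step a share of the current dose: 1 − 0.8³ = 0.488, about 49%.

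Either is a substantial fall in amount, yet such a patient would still count as receiving a prescription at week 6.

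**4. What must a quantity model allow for?** Under the trial summary's window (the preceding interval), the interval lengths are

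- 6 − 0 = 6, 12 − 6 = 6, 26 − 12 = 14 and 52 − 26 = 26 weeks;
- × 7 = 42, 42, 98 and 182 days.

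An unchanged 1 DDD/day (an illustrative value) gives totals of 42, 42, 98 and 182 DDD, but 1.00 DDD/day at every visit. If 3.1.4 and 3.5 were instead read as cumulative from baseline, the windows would be 42, 84, 182 and 364 days. Under either reading they are unequal.

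This does not bias the comparison between arms at a given visit. It does affect a model across visits. A constant difference of *d* DDD/day appears in raw totals as 42*d*, 42*d*, 98*d* and 182*d*, which a mean-difference model would register as a group-by-time interaction. With a log link and categorical time, interval length is constant within a visit and is absorbed by the visit effects, so the group ratios do not change.

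**The case against.** The strongest reply is that the defect is an omitted definition rather than an untestable objective. The plan already turns a broadly stated outcome into a binary one at the analysis stage: the trial summary and 3.1.2 name EQ-5D-3L without a dichotomy, and sections 3.5 and 10.3.3 supply one. A DDD cut-point would be the same step and would keep the logistic model. Part of this stands, and it is why the point is limited to 3.1.4 as worded and why a cut-point is offered below as an alternative. It does not rescue the present text, because no cut-point is given and adding one changes the question asked.

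A second reply is that a per-day scale or offset is redundant in a log-link model with time as a category. That is correct for that model. But section 10.3.3 allows a random slope for time, which treats time as numeric, and a mean difference is one of the possible effect measures. In those cases interval length matters, and elsewhere the adjustment does no harm.

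A third is that baseline adjustment has nothing to do with the mismatch. That is true; it is an inexpensive gain and the point does not depend on it.

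Finally, section 10.3.3 says the secondary analyses are not powered and are hypothesis generating. This limits the consequences, but it does not make a logistic model applicable to a quantity.

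**Conclusion.** The concern holds. Of the three endpoints that section 10.3.3 declares binary, one, assessed at four visits, is a quantity with no stated dichotomy. The assigned model and odds ratio do not fit it, and objective 3.1.4 cannot be tested as worded. This rests on the endpoint definitions alone and needs no numerical assumption; the 1 DDD/day figure and the taper arithmetic are illustrations.

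The prescribing window is a smaller matter. The trial summary defines it, and 3.1.4 and 3.5 do not repeat it, so this is a gap to fill rather than a contradiction.

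The point should be fixed, but it reaches only one of four secondary objectives and touches neither the primary analysis nor the sample size.

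**What to change.** 1. In 10.3.3, limit the binary/logistic sentence to self-reported discontinuation and the two EQ-5D-3L classifications.
2. Add a model for DDD prescribed: a longitudinal mixed model suited to a skewed quantity with zeros, for example with a log link. Keep the planned patient and general practitioner random effects and the group, time and group-by-time terms. Report a rate ratio or mean difference with 95% confidence interval.
3. Express the outcome as DDD per day, or use log interval length as an offset, and state whether time is categorical or linear.
4. Repeat the trial summary's preceding-interval window in 3.1.4 and 3.5.
5. As a refinement, adjust for prescriptions in the 6 months before entry, which section 7.6 already collects.

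Alternatively, keep the logistic model, pre-specify a DDD cut-point and reword 3.1.4 and 3.5 so that the hypothesis concerns the proportion beyond it.

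Either route costs a few sentences of text and needs no new data. The choice should be made before outcome data by arm are seen.
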